### ***Calculations***

- Percent Flow Mediated dilation = %FMD = LDp – LDb / LDb \* 100
  - LDp = Lumen diameter post-inflation; LDb = Lumen diameter baseline
- Reactive Hyperemia = Vp – Vb / Vb \* 100
  - Vp = Doppler velocity post-inflation; Vb = Doppler velocity baseline
- Sheer Rate (SR) = Vp/LDp (use mean velocity)

### **Venous Structure and Function**

Bilateral lower extremity (both legs) duplex ultrasound, utilizing 2D and Doppler, will be performed to assess the deep and superficial veins for venous insufficiency, varicosities, and/or valvular reflux. The study will be performed with the subject in the supine, steep reverse Trendelenberg position (bed tilted with head higher than the level of the heart and feet below level of the heart) with slight abduction of the leg at the knee to expose the groin region. A rapid tourniquet inflator/deflator system will be used to augment distal venous flow with consistent, reproducible effort throughout each segment of the limbs to calculate reflux time (reverse flow), if present. These maneuvers will be performed bilaterally in the common femoral vein, femoral vein, popliteal vein, posterior tibial vein, peroneal vein, proximal (thigh) and mid (upper calf) greater saphenous vein. In addition, the neck veins (internal jugular) and deep groin vein (common femoral) will be imaged to measure IMT (wall thickness), distensibility (wall stiffness), and acquire pulsatility index (blood flow velocity). Finally, the veins of the legs will be assessed for presence of DVT, acute or chronic, by light manual compression on the skin by the transducer to collapse the vein walls.

### **Venous Cannulation**

An 18 gauge catheter will be placed in each participant's antecubital vein and will be connected to a pressure monitor. Venous pressures will be monitored prior to beginning exercise and then every minute during exercise and after exercise during the recovery period (5 minutes). Venous pressures measured using a peripheral venous line has previously been shown to be reflective of central venous pressure in Fontan patients (Milhoan et al., 2004).

### **Spirometry**

Spirometry testing will be performed prior to the maximal exercise testing at visits 1, 2, and 3. Full spirometry testing will be performed including FVC/FEV1/Flows at 25% and 75% (FEF 25-75%). The predicted forced expiratory volume in 1 second (FEV1) will be calculated. This will be then used to calculate their maximum voluntary ventilation (MVV) with the following calculation: MVV = FEV1 x 40.

## Maximal Exercise Testing/Ramp Protocol

The {ParvoMedics Exercise cart with Blue Cherry software} will be used for cardiopulmonary exercise testing in all cases. The equipment will be calibrated and operated to the standards specified in the ATS/ACCP (2003) guidelines. Participants will initially sit at rest on the electromagnetically-braked cycle ergometer for three minutes while baseline cardiopulmonary variables are recorded (baseline phase). This will be followed by three minutes of unloaded cycling at a cadence of 60 rpm, after which the power output will be increased by 15 Watts per minute until the limit of tolerance. Talking to the study subjects will be kept to a minimum. Participants will be asked to maintain a cadence of 60 rpm throughout the test until volitional intolerance. The power output will be immediately reduced to zero and the cardiopulmonary variables monitored for at least 5 minutes (recovery phase). Transcutaneous CO2 monitoring will be done throughout the exercise test. Venous pressures will be monitored during exercise as described above (see Venous Cannulation).

The Innocor system (Innovision, Odense, Denmark) will be used to assess noninvasive cardiac output (CO) measurements based on the Inert Gas Rebreathing (IGR) method. Innocor is in clinical use at this institution and forms part of routine clinical exercise testing. The IGR method is based on the perfusion-related change in alveolar concentration of a soluble inert gas inspired from a closed system. A second insoluble marker gas is used for the determination of lung volume. The Innocor device consists of a closed system, including a three-way automatic respiratory valve connecting a facemask; a rebreathing bag, which is filled before commencement of the rebreathing maneuver to a calibrated volume; and an infrared photoacoustic gas analyzer. The inspired gas of this system contains 90% room air, whereas the remaining 10% is composed of a mixture of oxygen with 5% nitrous oxide (N2O) and 1% sulfur hexafluoride (SF6), resulting in inspired concentrations of 0.5% N2O as soluble and 0.1% of SF6 as non-soluble component. The soluble component of the inspired gas is absorbed by the pulmonary blood flow with an absorption rate proportional to the pulmonary blood flow. In the absence of shunts, pulmonary blood flow is equivalent to CO. SF6, as non-soluble component of the inspired gas, remains unaffected by pulmonary blood flow and allows determination of lung volumes. For the measurement, patients must breathe the gas mixture from the closed system during a period of a half minute. The components of the test gas as well as the expired carbon dioxide (CO2) are continuously and permanently recorded at the mouthpiece and computed by a photoacoustic gas-analyzer.

The Innocor system will be used to assess pulmonary blood flow at rest and at peak exercise, i.e. 2 time points. Because steady breathing with constant amplitude is required to obtain reliable measurements, all participants will be familiarized with the exercise protocol and practiced the rebreathing maneuvers before the test, and we will only obtain data with the Innocor system just prior to beginning the exercise test and at peak exercise to limit any confounding of the regular exercise test data, as switching from one mouthpiece to another is required and this will minimize inaccurate data during this transition.

## **Endurance Exercise Testing**

Exercise endurance is a highly sensitive measure of functional outcome following interventions (Oga et al., 2000; Borel et al., 2013). Two hours after ramp incremental exercise testing (CPET) a constant work rate exercise test will be performed to determine exercise endurance; 2 hours is sufficient for complete recovery of exercise endurance following prior exhaustive exercise (Ferguson et al., 2010). The primary outcome from this assessment is exercise duration; standard CPET variables will also be measured throughout to provide physiological interpretation for exercise endurance change. A power output corresponding to 80% of the peak power achieved during the ramp incremental test will be calculated. After ~ 3 minutes at unloaded cycling, the power will be increased abruptly to 80% peak power: The subject will be encouraged to continue for as long as possible and the duration recorded. The target duration for this exercise test at baseline is 4-7 minutes and is typically achieved at 80% peak power (van der Vaart et al., 2013). In the event that the exercise endurance test duration falls outside of this 'optimal' range at the first visit, the power output may be adjusted by 5 Watts (or 10% rounded to the nearest 5W, whichever is greater) and this adjusted power used for all subsequent tests.

Exercise endurance change, and well as change in "isotime" physiologic variables (comparison between physiologic values during active drug and placebo measured at the same time points during exercise), including central venous pressure and vo2, between tests with placebo and inhaled treprostinil will be calculated.

## **Shear Wave Elastography**

Liver stiffness will be measured using shear wave elastography. Shear wave elastography, also known as acoustic radiation force impulse (ARFI), is a recently U.S. FDA-approved ultrasound technology produced by all major US system manufacturers that employs an acoustic "push pulse" mechanism to create in vivo shear waves. The speed of the shear waves rises with increasing tissue stiffness such as with tissue fibrosis and hepatic congestion. Multiple ARFI pulses create color maps called elastograms indicative of the severity of tissue stiffness. The technology is nonionizing, noninvasive, potentially portable and lower in cost compared to MRI.

### **6.1. Process of Obtaining Informed Consent**

Consent will be obtained from all patients before any study related procedures are performed. The investigator or designated study staff will be available to answer any questions that the participant may have regarding procedures, risks and alternatives. The consent process will be documented on the informed consent progress note. A copy of the signed consent(s) will be kept in the patient's medical record and a copy will be provided to the patient.

### **6.2. Laboratory Assessments**

#### **6.2.1. Chemistry Parameters**

Metabolic panel (CMP), GGT, and CBC will be drawn at visit 2.

## 7. INVESTIGATIONAL AGENT

### 7.1. Description

Inhaled treprostinil is a prostacyclin vasodilator indicated for the treatment of pulmonary arterial hypertension (PAH) (WHO Group 1) to improve exercise ability through direct vasodilation of pulmonary and systemic arterial vascular beds. Treprostinil also causes inhibition of platelet aggregation. Bioavailability of inhaled treprostinil is estimated to be approximately 64-72%. Treprostinil is substantially metabolized by the liver with inactive metabolites excreted in urine and feces. Other pharmacokinetic and pharmacodynamic properties specific to the inhaled form of treprostinil are not well defined. Inhaled treprostinil is supplied as an ampule containing 1.74mg/2.9mL (0.6mg/mL) and the placebo will contain 0mg/2.9ml.

### 7.2. How Supplied

For this study, Tyvaso® (treprostinil) inhalation system and solution will be supplied by United Therapeutics, Inc. for the investigational uses of the drug. United Therapeutics, Inc. will provide Tyvaso 4 Pack Carton with one foil pouch containing four 2.9 mL ampules. Each ampule contains 1.74 mg treprostinil (0.6 mg per mL).

### 7.3. Storage

Tyvaso® (treprostinil) inhalation solution is supplied in 2.9 mL clear LDPE ampules packaged as four ampules in a foil pouch. Tyvaso is a clear colorless to slightly yellow solution containing 1.74 mg treprostinil per ampule at a concentration of 0.6 mg/mL.

Ampules of Tyvaso are stable until the date indicated when stored in the unopened foil pouch at 25°C (77°F), with excursions permitted to 15-30°C (59-86°F) [see USP Controlled Room Temperature]. Once the foil pack is opened, ampules should be used within 7 days. Because Tyvaso is light-sensitive, unopened ampules should be stored in the foil pouch. Any ampules from an opened pack should be used within 7 days or thrown away.

### Proposed Dose

Inhaled treprostinil (1.74mg/2.9mL) or matching placebo will be dispensed and maintained through the CCHMC investigational pharmacy and administered using the Tyvaso inhalation system. A dose of 18mcg (3 breaths) or placebo (3 breaths) will be administered prior to the vascular function assessment (test dose to assess adverse effects), prior to the maximal exercise test (at minimum, 2 hours post initial dose) and then again prior to the endurance exercise test.

## **8. DATA COLLECTION AND MANAGEMENT**

### **8.1. Data Collection**

All data will be recorded on study-specific case report forms (CRFs). Participants will be given a study identification number that will be reported on all CRFs and source documents.

Demographic data, diagnoses, prior interventions, both surgical and cardiac catheterization based intervention will be collected. Imaging reports will be reviewed for evidence of anatomic and specific hemodynamic problems of the circuit prior to recruitment of potential participants, thereby allowing us to exclude those patients. Hemodynamic characteristics and ventricular functional characteristics will be recorded at latest follow-up.

### **8.2. Data Management**

Data management will be handled using CCHMC's standard operation procedures and guidelines. Data will be collected by designated research coordinator(s) and the physicians participating in the study. Only study personnel will have access to data. Data will be indexed by a study-specific subject number; the key which links this number to identifying information will be stored in a separate, secure location. All study data will be stored in a secure, confidential database.

## **9. DATA ANALYSIS**

### **9.1. Study Endpoints**

The primary endpoint is exercise endurance time (seconds).

The secondary endpoints are the following:

- Peak VO2
- Ventilator equivalent for CO2 at the lactate threshold
- Oxygen uptake efficiency slope
- Lactate threshold
- Pulmonary blood flow
- Pulse wave velocity
- Augmentation Index
- Shear wave elastography (measure in velocity [m/s]), the mean of 10 measurements will be taken.
- Safety endpoints will include: a drop in systolic systemic blood pressure of greater than 30 mm Hg if SBP >120mm Hg, or a drop in BP to <90 mm Hg if resting BP is less than 120mmHg.

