## **4. STUDY DESIGN**

### **4.1. Study Description**

This will be a prospective, randomized, double-blinded placebo controlled, crossover trial. Following recruitment and informed consent, each participant will undergo three study visits, including baseline testing (visit 1), followed by two sets of exercise and vascular function tests (visit 2 and visit 3) at CCHMC. Twenty-six patients will be enrolled in this study.

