### Baseline visit (Visit 1)

- Informed Consent
- Review of Demographics, Medical history, and Medications
- Urine pregnancy testing (for females of childbearing potential)
- Baseline vitals (heart rate, blood pressure, oxygen saturation, height and weight)
- Maximal cardiopulmonary exercise testing/Ramp protocol (including spirometry).
- Venous structure and function testing
- Light meal and rest period.
- Endurance testing at 80% peak exertion to assess baseline measures. (2 hours following maximal exercise testing)
- Adverse event monitoring

Visit 1 is anticipated to take 5-6 hours to complete. At the end of Visit 1, participants will be randomized to one of the two treatment sequences:

1. Treprostinil (Visit 2): placebo (Visit 3) or
2. Placebo (Visit 2): treprostinil (Visit 3).

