### Visit 2 (Visit 2 will occur 1-2 weeks (+/- 3 days) after Visit 1)

- Insertion of venous cannula will be placed early in the visit to be used for taking venous pressure during the exercise testing.
- Vital signs (heart rate, blood pressure, oxygen saturation, height and weight)
- Blood drawn for metabolic panel (CMP), GGT, CBC (Drawn once at visit 2 or visit 3)
- Review of Concomitant Medications
- Urine pregnancy testing
- Resting ECG
- First dose of treprostinil OR placebo, as determined by the randomization following Visit 1.
- Participant blood pressure will be monitored for  $\frac{1}{2}$  hour (immediately, 15 min, and 30 min.) following the initial dose of treprostinil or placebo on a particular study day.
  - If systolic BP drops below 90 mm Hg or drops  $\geq 30$  mm Hg from the baseline, the participant's blood pressure will be monitored until return to above these thresholds. If baseline systolic blood pressure is below 90 mm Hg, then

the low threshold for additional monitoring will be 85 mm Hg for these participants.

- Study staff monitoring the blood pressure will consult with the PI or MD subI should a drop in blood pressure meeting these thresholds occur. Patient will continue with the investigation at the discretion of the PI or MD subI.
- Shear Wave Elastography (for liver stiffness)
- Vascular function assessment (Pulse Wave Velocity [PWV] and brachial Flow Mediated Dilation [FMD], already in use in this institution (described below).
- If the participant tolerated the 1st dose of treprostinil or placebo, (i.e no clinically significant drop in blood pressure or unexpected AEs deemed by the PI or MD subI to be related to study drug that would preclude the patient from continued participation) they will receive a 2nd dose of their assigned treatment (at least 2 hours after the first dose).
- If the patient did not experience a significant drop in blood pressure (as defined previously) following the 1st dose, then no further blood pressure monitoring will be required prior to the exercise test.
- If the participant experienced a drop in blood pressure (as defined previously) following the 1st dose, then blood pressure will be monitored for ½ hour (immediately, 15 min, and 30 min.) following the 2nd dose of treprostinil or placebo.

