f Blood pressure will be monitored for 30 minutes post study drug administration (immediately, 15 min, and 30 min).. Window for blood pressure measurements is +/- 3 minutes. If no drop in BP below threshold levels following previous study drug administration, then BP will not be monitored for subsequent doses. Threshold levels for additional monitoring are a drop in systolic pressure below 90 mm Hg (or 85 mg Hg if baseline was  $\leq$  90 mm Hg) or drop of  $\geq$  30 mm Hg from baseline.

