## **9.2. Statistical Analyses**

Demographic and clinical characteristics of the patient population will be summarized using means and standard deviations or medians and interquartile ranges for continuous variables and frequency and percent for categorical variables.

The exercise endurance time (in seconds) will be compared between the two treatments (i.e. Treprostinil and placebo) using an analysis of variance (ANOVA) model for crossover designs. The terms in the model will include sequence, subject within sequence, treatment. Data will be assessed to determine if the normality assumption is plausible. If the normality assumption is not met, transformations will be applied in an attempt to satisfy the assumption (i.e. log, square root, rank). P-values  $<0.05$  will be considered significant.

Secondary outcome variables are continuous and will be analyzed using the ANOVA model for crossover designs as described for the primary outcome variable. For secondary outcome variable in which a baseline measure is taken, the change from baseline value will be used as the outcome variable and will be compared between treatment groups. Normality will be assessed and appropriate transformations used, if needed to satisfy the assumptions of the model. P-values  $<0.05$  will be considered significant.

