## **9.3. Sample Size Calculation**

Sample size calculations are based on published literature {Oga et. al. Chest 2003 Jun; 123(6): 1810-6.}. The SD of treatment effect for exercise endurance time is estimated to be 65 second. A sample size of 26 patients is required to have 80% power to detect a change of 37 second using a two-sided test at  $\alpha=0.05$ . This sample size will also provide 80% power to detect an approximate 0.5 m/s change in liver stiffness assuming an SD of 0.75 m/s using the two-sided test at  $\alpha=0.05$ .

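### Systolic pressure is recorded after Dose 1 on both treatments in every participant, but the plan names only a yes/no threshold crossing and no comparison of the size of the fall

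*Combined protocol and SAP*

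**What the plan says.** **Collection.** Section 6, Visit 2, lists vital signs before dosing and then pressure over half an "hour (immediately, 15 min, and 30 min.) following the initial dose of treprostinil or placebo on a particular study day". Visit 3 repeats the Visit 2 procedures on the other treatment. Footnote f to Table 1 gives the same schedule: "Blood pressure will be monitored for 30 minutes post study drug administration (immediately, 15 min, and 30 min"). It adds that later doses are monitored only if a threshold was crossed after the previous dose. Dose 1 is therefore the one complete series on both treatments.

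**Endpoint.** The last item in the secondary endpoint list of Section 9.1 says what the safety endpoints will include. It names one: "a drop in systolic systemic blood pressure of greater than 30 mm Hg if SBP >120mm Hg, or a drop in BP to <90". The second limb, also in mm Hg, applies where resting pressure is below 120.

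**Analysis.** Section 9.2 states: "Secondary outcome variables are continuous and will be analyzed using the ANOVA model for crossover designs as described for the primary outcome variable". It adds that change from baseline is the outcome where a baseline is taken. It gives no method for comparing a binary outcome.

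**Pharmacology.** Section 7.1 describes direct vasodilation of systemic as well as pulmonary arterial beds.

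**The concern.** A systemic pressure effect is expected from the drug's mechanism, and the crossover yields a within-patient, placebo-controlled measurement of it. The named endpoint keeps only whether a line was crossed, and the line depends on resting pressure. By the 9.1 rule, 92 to 89 (a fall of 3) is an event, while 118 to 90 (a fall of 28) and 125 to 95 (a fall of 30) are not. The last two sit exactly on the boundary, and 1 mm Hg more would make either an event. They still show that the event depends on closeness to 90 as well as on the size of the fall.

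At stake is how the safety result is read. Section 10.1 foresees telling cardiologists about participants with hemodynamic improvement so that longer-term therapy can be discussed. Most efficacy measures in 9.1 have a planned comparison on a continuous scale. Similar small event counts on drug and placebo could be taken as reassurance about pressure when the paired readings show an average fall.

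**Working it through.** **1. Design inputs and the plan's own figure.** Section 4.1: "This will be a prospective, randomized, double-blinded placebo controlled, crossover trial". Section 9.3: "The SD of treatment effect for exercise endurance time is estimated to be 65 second" and "A sample size of 26 patients is required to have 80% power to detect a change of 37 second using a two-sided test at" 0.05. Reading 65 s as the SD of the within-patient difference:

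- Normal approximation: ((1.960 + 0.842) × 65/37)² = 24.2, so 25 patients.
- Noncentral t: 79.7% power at n = 26, with 27 needed to pass 80%.

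The stated 26 is reproduced to within one patient, so a paired comparison on 26 participants is the right frame.

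**2. Degrees of freedom.** With complete data, the 9.2 model (sequence, subject within sequence, treatment) leaves 52 − 1 − 1 − 24 − 1 = 25 residual df. Its treatment test is the paired t-test.

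**3. What a test of crossings would need.** The plan names no test. If exact McNemar were used, only discordant participants count:

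- 5 discordant, all on drug: p = 2 × (1/2)⁵ = 0.0625.
- 6 discordant, all on drug: p = 2 × (1/2)⁶ = 0.031.

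At least 6 one-way discordant participants out of 26 are needed. This step requires no SBP assumption.

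**4. Precision of the continuous comparison.** The 95% half-width is t(0.975, 25) × SD/√26 = 2.06 × SD/5.10. For an assumed SD of the difference of 10 mm Hg it is ±4.0 mm Hg. The mean difference detectable with 80% power is 4.6, 5.7, 6.9 or 8.6 mm Hg for an SD of the difference of 8, 10, 12 or 15.

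**5. Power under assumed SBP values.** The documents give no resting SBP, SD or expected fall. Two sets of assumptions were simulated, each giving every participant the same extra mean fall on drug.

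*Set A, maximum fall:* resting mean 105-120, SD 12, visit noise SD 5; mean maximum fall 3 on placebo; SD of the fall 6-10 within each visit; resting values below 90 not scored as events. For an extra 8 mm Hg at SD 8:

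- Event rates are 3-11% on placebo and 10-28% on drug.
- Exact McNemar power is 2-21%.
- For the paired t-test, the SD of the difference is 8√2 = 11.3 and the noncentrality is 8/(11.3/5.10) = 3.6, giving about 93%.
- Over extra falls of 5-10 mm Hg and SD 6-10, power is 0-45% for events and about 40-100% for the fall.

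*Set B, events on the lowest of three readings, continuous analysis on their mean:* resting mean 105-120, between-patient SD 10 or 13, SD of the paired difference about 8.7 or 13.3 (12 settings).

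| Extra mean fall | Crossings, exact McNemar | Size of fall, paired t |
|---|---|---|
| 5 mm Hg | 0-15% | 45-81% |
| 8 mm Hg | 0.5-42% | 83-99.7% |
| 10 mm Hg | 3-64% | 96-100% |
| 15 mm Hg | 39-97% | about 100% |

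For 5-10 mm Hg, crossings have under 50% power in 34 of 36 scenarios. Both exceptions are a 10 mm Hg fall with mean resting SBP 105. Mid-p McNemar raises the 10 mm Hg range to 8-75%.

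**6. Uneven effect.** If the same 8 mm Hg average is concentrated in 25-30% of participants (resting mean 112-120, SD of the fall 8), power is about 32-36% for crossings and 58-67% for the fall.

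**7. Thresholds side by side.**

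- Section 9.1 requires a fall of more than 30 from above 120, or a value under 90 from below 120. Exactly 120 is unassigned.
- The Visit 2 text, footnote f and the Blood Pressure Monitoring table use a fall of 30 or more from any baseline, or a value under 90, with 85 for low baselines.
- The 85 rule applies at a baseline of 90 or less in footnote f, but below 90 in the table.

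**The case against.** **McNemar is not in the plan.** That is correct. Section 9.2 specifies no test for the event, so the power figures describe what a test could do, not what the plan says it will do. If the event is only counted, there is no treatment comparison of it at all.

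**Section 9.2 might already cover SBP change.** The safety item sits in the secondary list, and 9.2 sends secondary variables to the ANOVA as change from baseline. The item itself defines a crossing, however, so the text is ambiguous. A reader might infer that the plan rules out any analysis of the fall. The supportable statement is that it does not clearly provide one.

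**It is not the only safety information.** This stands. Section 9.1 says what safety endpoints will include, Section 11 has adverse events recorded and classified, and Section 13 has a board reviewing safety data. The crossing is the only safety endpoint named.

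**The threshold answers its own question.** Also right. Counting individuals with large or low-pressure falls is a valid safety summary, and this is a pilot whose objectives do not include estimating the mean pressure effect. Each participant is their own control, so closeness to 90 costs information and does not by itself bias the comparison. The mean fall complements the count.

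**The power gap depends on assumptions.** It does. A reader might infer that the threshold endpoint has almost no ability to separate drug from placebo, or that a clear fall would usually be missed. Neither is supported in general: at 15 mm Hg crossings reach 39-97% in Set B, and an uneven effect shrinks the gap.

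**Conclusion.** The concern holds in limited form. Section 9 leaves a complete paired SBP series after Dose 1 without a clearly specified comparison and names only a binary crossing tied to resting pressure. That much rests on the documents alone.

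The size of the loss rests on assumed SBP values. For uniform extra mean falls of about 5-10 mm Hg, a test of crossings would have roughly 0-60% power against roughly 40-100% for a paired continuous analysis. The upper end for crossings arises when mean resting SBP is near 105.

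The primary endpoint is unaffected. This is a worthwhile, low-cost addition to the safety analysis and does not make the threshold endpoint wrong.

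**What to change.** - **Section 9.1:** add as a safety endpoint the maximum SBP fall within 30 minutes of Dose 1, defined as pre-dose SBP at that visit minus the lowest of the three post-dose readings.
- **Section 9.2:** report the treprostinil-placebo mean difference in that fall, with its 95% CI, from the crossover ANOVA already specified. State that the threshold event is reported as a descriptive count by treatment.
- **Consistency:** reconcile the 9.1 thresholds with those in the Visit 2 text, footnote f to Table 1 and the Blood Pressure Monitoring table. No monitoring rule or threshold is proposed here.

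The cost is a few sentences and one more run of an existing model, with no new data, visits or staff. The downside is one more safety estimate to report. It covers Dose 1 only, because readings after Doses 2 and 3 are conditional on an earlier crossing, so it says nothing about the doses given before exercise.

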## Blood Pressure Monitoring

Blood Pressure will be monitored following administration of treprostinil or placebo dosing as shown below. Additional blood pressure monitoring may occur at any time during the procedure at the discretion of study staff for patient safety.

[figure not shown]

If Baseline Systolic BP is:	Threshold for additional monitoring is:	Action Taken
≥90 mg Hg	drop in systolic BP to < 90 mm Hg OR drop in systolic BP of ≥ 30 mm Hg from baseline	Monitor BP until return to baseline PI or MD subI assess if patient can continue Monitor BP at next dose: immediately, 15 min, 30 min
<90 mg Hg	drop in systolic BP to < 85 mm Hg OR drop in systolic BP of ≥ 30 mm Hg from baseline	Monitor BP until return to baseline PI or MD subI assess if patient can continue Monitor BP at next dose: immediately, 15 min, 30 min

[figure not shown]

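### Minor: the blood-pressure safety endpoint in 9.1 leaves a resting SBP of exactly 120 unclassified and is unworkable below 90, and Table 1 footnote f conflicts with the monitoring rule at a baseline of exactly 90

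*Combined protocol and SAP*

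**What the plan says.** Section 9.1 lists the safety endpoint as the last bullet under the secondary endpoints. It has two branches:

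- upper: "a drop in systolic systemic blood pressure of greater than 30 mm Hg if SBP >120mm Hg"
- lower: "a drop in BP to <90 mm Hg if resting BP is less than 120mmHg"

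Section 6 has a separate rule that triggers extra blood-pressure monitoring. The Visit 2 text gives low baselines their own limit: "If baseline systolic blood pressure is below 90 mm Hg, then" "the low threshold for additional monitoring will be 85 mm Hg for these participants". The Blood Pressure Monitoring table agrees. Its row for baselines of 90 or more is triggered by SBP below 90 or a fall of at least 30 mm Hg. Its row for baselines below 90 reads "drop in systolic BP to < 85 mm Hg OR drop in systolic BP of ≥ 30 mm Hg from baseline".

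Table 1 footnote f restates the rule with a different cut: "or 85 mg Hg if baseline was" is followed by a less-than-or-equal sign and 90.

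On analysis, Section 9.2 says "Secondary outcome variables are continuous and will be analyzed using the ANOVA model for crossover designs". Its only mention of frequencies and percentages is in the sentence beginning "Demographic and clinical characteristics of the patient population will be summarized".

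**The concern.** This is the only safety endpoint that 9.1 names, and the study drug is described in 7.1 as a vasodilator of the systemic as well as the pulmonary arterial bed. The definition should therefore give one answer for every resting value. It fails to do so in two places: at exactly 120, where neither branch applies, and below 90, where the wording allows two readings with opposite results. Two analysts could report different event counts from the same readings, and the choice between readings could be made after the data are seen.

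The footnote f conflict is of another kind. It concerns a bedside trigger, not the endpoint. Staff working from the schedule table and staff working from the visit text would act differently for a participant whose baseline is exactly 90.

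**Working it through.** **Inputs.** The endpoint is from 9.1. The monitoring rule is from the Section 6 Visit 2 text and the Blood Pressure Monitoring table. The variant is from Table 1 footnote f. Let b be the resting SBP and f the fall, both in whole mm Hg. I take the SBP in the upper branch and the BP in the lower branch both to mean resting systolic pressure. The plan states no figure of its own to reproduce here.

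**Rules as formulas.**

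- 9.1, literal: event if (b > 120 and f > 30) or (b < 120 and b − f < 90).
- 9.1, crossing 90: as above, but the second part also needs b ≥ 90.
- Section 6 monitoring: trigger if f ≥ 30, or b − f < 90 when b ≥ 90, or b − f < 85 when b < 90.
- Footnote f: as Section 6, but with 85 applied when b ≤ 90.

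**Smallest fall that counts (mm Hg).**

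| Resting SBP | 9.1 literal | 9.1 crossing 90 | Section 6 | Footnote f |
|---|---|---|---|---|
| 85 | 1 | never | 1 | 1 |
| 86 | 1 | never | 2 | 2 |
| 87 | 1 | never | 3 | 3 |
| 88 | 1 | never | 4 | 4 |
| 89 | 1 | never | 5 | 5 |
| 90 | 1 | 1 | 1 | 6 |
| 119 | 30 | 30 | 30 | 30 |
| 120 | never | never | 30 | 30 |
| 121 | 31 | 31 | 30 | 30 |

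**At 120.** A fall from 120 to 60 is not an event under 9.1, although 119 to 89 is (f = 30) and 121 to 90 is (f = 31). Either repair gives the same answer. In the upper branch, f > 30 from 120 means SBP ≤ 120 − 31 = 89. In the lower branch, SBP < 90 also means SBP ≤ 89.

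**Below 90.** On the literal reading, 89 to 88 is an event. On the crossing reading, 89 to 50 is not. Among resting values below 120, the literal reading departs from the Section 6 rule only at 86–89. At 85 and lower, both count a 1 mm Hg fall; from 90 to 119 they agree for every fall.

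**Above 120.** The endpoint (f > 30) and the monitoring rule (f ≥ 30) differ only at f = 30. These are two rules with two purposes, and I do not count this as a defect.

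**Footnote f.** It differs from the rest of Section 6 only at b = 90 with f = 1 to 5 (readings of 85 to 89). Section 6 triggers monitoring there and the footnote does not.

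**Size.** The documents give no SBP distribution, so this step rests on assumptions. There are 26 × 2 = 52 dosing visits. Suppose resting SBP is normal, recorded to the nearest mm Hg, with mean 105 to 120 and SD 10 to 15. The expected number of visits starting at a value v is 52 × [Φ((v + 0.5 − mean)/SD) − Φ((v − 0.5 − mean)/SD)]. Over that range:

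- exactly 120: 0.7 to 2.1 visits
- 86–89: 0.04 to 2.8 visits
- exactly 90: 0.02 to 0.84 visits

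If 1% to 10% of visits also had a fall above 30 mm Hg, the gap at 120 would miss between 0.67 × 0.01 = 0.007 and 2.07 × 0.10 = 0.21 events in the whole trial.

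**The case against.** The strongest reply is that this is copy-editing. The gap at 120 is a slip with one evident meaning, since both branches agree there. Section 9.1 introduces its safety endpoints in terms that need not be exhaustive. The low-baseline problem touches few values, and footnote f changes no analysis. Much of this stands, and it is why the point is minor. What it does not answer is that 9.1 as written leaves one resting value unclassified, that its two readings below 90 give opposite results, and that Section 6 states its trigger in two ways.

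A reader might infer more than the documents support:

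- *That 9.1 has no rule below 90.* It has one: a resting SBP of 88 is below 120, so the lower branch applies. The fault is that the rule is unworkable there.
- *That 9.1 contradicts the 85 mm Hg limit at all low baselines.* The literal reading differs from it only at 86–89. The 85 limit is also a monitoring trigger, so this is a mismatch between two rules and not a contradiction.
- *That a participant starting at 120 goes unprotected.* A fall of 30 mm Hg or more still triggers monitoring and physician review under Section 6, and the event can be recorded as an AE under 11.1.
- *That a yes/no endpoint will be put through the crossover ANOVA.* Its place in the secondary list allows that reading, but the bullet is labelled as safety, and the ANOVA sentence describes continuous outcomes. No summary is stated for it. In a 26-patient pilot that is missing detail, and nothing in the plan calls for a paired significance test.
- *That the endpoint should be scored only on the readings after Dose 1.* Section 9.1 makes no such restriction. It would discard falls after Doses 2 and 3, when Section 6 schedules readings for participants who have already had a drop.

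**Conclusion.** The point holds as a minor error in the current text. The 9.1 endpoint omits a resting SBP of exactly 120 and gives either a trivial event or no possible event below 90, depending on the reading. Footnote f conflicts with the Visit 2 text and the monitoring table at a baseline of exactly 90, for falls of 1 to 5 mm Hg. These findings follow from the wording and need no assumption beyond whole-number readings and reading BP in 9.1 as resting systolic pressure.

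The size does rest on assumptions. Under the SBP distributions and fall rates tried above, the gap at 120 costs fewer than one event, and at most about three of the 52 dosing visits start at 86–89. The actual numbers are unknown. The primary endpoint, the sample size, AE/SAE reporting and participant oversight are unaffected.

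**What to change.** - **9.1, at 120:** make one boundary inclusive, either at least 120 in the upper branch or at most 120 in the lower. The choice makes no difference in whole mm Hg.
- **9.1, below 90:** for a resting SBP below 90, define the event by the Section 6 table: SBP below 85 or a fall of at least 30 mm Hg. From below 90, a 30 mm Hg fall always ends below 60, so the 85 limit decides.
- **Table 1 footnote f:** change the cut from 90 or less to below 90.
- **9.2, tidy-up only:** say that this endpoint is reported as counts and percentages by treatment and is not part of the ANOVA.

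The repaired 9.1 then differs from the monitoring table only at a fall of exactly 30 mm Hg from 120 or above. It still counts a 1 mm Hg fall from 90, and from 85 or below, as the monitoring table does. If the investigators do not want that, they can add a minimum fall of their choosing.

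The cost is a few words in 9.1, 9.2 and the footnote. No new data are needed, and readings already recorded can be rescored.
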